### 8.3.2.2 Analysis of Key Secondary Efficacy Endpoint

#### **Absolute change in CFQ-R respiratory domain score from study baseline to the average of the Week 4 and Week 8 measurements in each Treatment Period**

Analysis for the absolute change from study baseline in CFQ-R respiratory domain (Pooled 'Children Ages 12 and 13' Version and 'Adolescents and Adults' Version) score to the average of Week 4 and Week 8 scores in each treatment period will be similar to the primary analysis of the primary efficacy endpoint. However, ppFEV1 at study baseline will be replaced by CFQ-R respiratory domain score at study baseline in the model.

The estimated mean of absolute change from study baseline in CFQ-R respiratory domain score to the average of Week 4 and Week 8 scores will be presented along with the 95% CI and the 2-sided *P* value. Similarly, the estimated differences between treatment groups and the associated 95% CI and *P* value will be presented.

[figure not shown]
The raw value and absolute change from study baseline in CFQ-R respiratory domain score at post-baseline visits (Weeks 4 and 8) will be summarized by treatment group using descriptive statistics. Similar descriptive statistics will also be presented for average CFQ-R respiratory domain score at Weeks 4 and 8 and the average absolute change from study baseline in CFQ-R respiratory domain score at Weeks 4 and 8. The cumulative distribution plot will be created for this endpoint.

### 8.3.2.3 Multiplicity Adjustment

There are 3 potential treatment comparisons for the primary and key secondary endpoint: TEZ/IVA versus placebo, IVA monotherapy versus placebo, and TEZ/IVA versus IVA monotherapy. The testing strategy will be limited to the comparison of TEZ/IVA versus placebo and IVA monotherapy versus placebo. To control for multiplicity of endpoints and treatments (the probability of Type 1 error), each endpoint will be assessed sequentially using a gatekeeping approach where statistical significance can be claimed for the key secondary endpoint only if the primary endpoint meets the requirements for significance. Additionally, as there are two treatments for each endpoint, the gatekeeping approach will also be applied, i.e., IVA monotherapy for a given endpoint can achieve significance only if the comparison for TEZ/IVA for the same endpoint is significant (Figure 8-1). For each endpoint, and for each treatment group, the comparison with placebo will be conducted using a significance level (alpha) set at 0.05 (2-sided).

**Figure 8-1 Testing Strategy for the Primary and Key Secondary Endpoint**

IVA: ivacaftor; TEZ: VX-661; PBO: placebo; ppFEV1: percent predicted forced expiratory volume in 1 second; CFQ-R: Cystic Fibrosis Questionnaire–Revised (respiratory domain); Avg: Average

### 8.3.2.4 Analysis of Other Secondary Efficacy Endpoints

#### **Relative change in ppFEV1 from study baseline to the average of the Week 4 and Week 8 measurements in each Treatment Period**

Analysis of this variable will be similar to the primary analysis of the primary efficacy endpoint.

The estimated mean of relative change from study baseline in ppFEV1 to the average of Week 4 and Week 8 measurements will be presented along with the 95% CI and the 2-sided *P* value. Similarly, the estimated differences between treatment groups and the associated 95% CI and *P* value will be presented.

In addition, summary statistics of the relative change from study baseline in ppFEV1 at post baseline visits (Day 15, Week 4 and 8) as well as the average relative change from study baseline in ppFEV1 at Weeks 4 and 8 will be presented by treatment group. The cumulative distribution plot will not be created for this endpoint.

#### **Absolute change in sweat chloride from study baseline to the average of the Week 4 and Week 8 measurements in each Treatment Period**

Analysis of this variable will be similar to the primary analysis of the primary efficacy endpoint. However, ppFEV1 at study baseline will be replaced by sweat chloride at study baseline in the model.

The estimated mean of absolute change from study baseline in sweat chloride to the average of Week 4 and Week 8 measurements will be presented along with the 95% CI and the 2-sided *P* value. Similarly, the estimated differences between treatment groups and the associated 95% CI and *P* value will be presented.

In addition, raw value and absolute change from study baseline in sweat chloride at post-baseline visits (Weeks 4 and 8) along with the average sweat chloride at Weeks 4 and 8 and the average absolute change from study baseline in sweat chloride at Weeks 4 and 8 will be summarized by treatment group using descriptive statistics. The cumulative distribution plot will not be created for this endpoint.

### 8.3.2.5 Sensitivity, Supportive, and Subgroup Analysis of Secondary Endpoints

No sensitivity, supportive, or subgroup analysis are planned for the secondary endpoints.

[REDACTED]

[REDACTED]

[REDACTED]

[REDACTED]

[REDACTED]

[REDACTED]

## 8.4 Safety Analysis

All safety analyses will be based on the set of data associated with the TE period for Treatment Period 1 and the TE period for Treatment Period 2. Safety analyses will use the Safety Set. Subjects will be analyzed according to the treatment they actually received in a given treatment period. For subjects receiving study drug from more than one treatment group in the same treatment period, the treatment group allocation will be the higher treatment group (TEZ/IVA > IVA monotherapy > Placebo). For safety analysis, the period baseline will be used.

The overall safety profile of study drug will be assessed in terms of the following safety and tolerability endpoints:

- Adverse events
- Clinical laboratory values (hematology, serum chemistry, coagulation studies, vitamin levels, lipid panel, and urinalysis)
- Standard 12-lead electrocardiograms
- Vital signs
- Pulse oximetry
- Postdose ppFEV1 and FEV1 (L) and change from predose (in subjects <18 years at screening).

The safety profile will also include the following safety-supporting data

- predose ppFEV1 and FEV1 (L) across visits
- Weight
- BMI.

Only descriptive analysis of safety will be performed; no statistical testing is planned.

For the purpose of safety analysis, the study period will be further divided into 3 segments per the definition of the treatment emergent (TE) period (Section 8.1):

- The **pre-treatment period** is the period after the informed consent/assent date and before the initial dosing of study drug in the study.
- The **treatment-emergent period** (TE period) is defined in Section 8.1.
- The **post-treatment period** is the period after the last date of TE period for Treatment Period 2 to the date of the last study record in the clinical database or the period between the end of TE period for Treatment Period 1 and the start of TE period for Treatment Period 2. For subjects who do not have Treatment Period 2, the period after the last date

of TE period for Treatment Period 1 to the date of the last study record in the clinical database will be considered as post-treatment period.

### 8.4.1 Adverse Events

For analysis purpose, AEs will be categorized as pretreatment AEs, treatment-emergent adverse events (TEAEs), or post-treatment AEs:

- **Pretreatment AE:** any AE that started before initial dosing of study drug in the study.
- **TEAE:** any AE that increased in severity or that was newly developed during the TE period for Treatment Period 1 or Treatment Period 2. If an AE started (or increased in severity) during a specific Treatment Period, this AE will be attributed to the treatment the subject was receiving during the Treatment Period.
- **Post-treatment AE:** any AE that increased in severity or that was newly developed beyond the TE period for Treatment Period 2, or between the TE periods for Treatment Period 1 and Treatment Period 2, or beyond the TE period for Treatment Period 1 for subjects who do not have Treatment Period 2.

For AEs with missing or partial start date, if there is no clear evidence that the AEs started (or increased in severity) before the first dose, the start date will be imputed to the first dosing date and the AE assigned to the treatment in Treatment Period 1. As an intermediate step for programming purposes, imputation rules for missing or partially missing AE start/end dates are defined in Section 10.7.

By relationship to the study drug regimen, TEAEs will be classified into the 4 categories:

- Not related
- Unlikely related
- Possibly related
- Related

By severity, TEAEs will be classified into the 4 categories:

- **Mild (Grade 1):** Mild level of discomfort and does not interfere with regular activities
- **Moderate (Grade 2):** Moderate level of discomfort and significantly interferes with regular activities
- **Severe (Grade 3):** Significant level of discomfort and prevents regular activities
- **Life-threatening (Grade 4):** Any adverse drug experience that places the subject, in the view of the investigator, at immediate risk of death

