## 6 STUDY DESIGN

### 6.1 Overview of Study Design

This is a Phase 3, randomized, double-blind, placebo-controlled, 2-period, 3-treatment, crossover, multicenter study in subjects aged 12 years and older with CF, heterozygous for the F508del-CFTR mutation, and a second allele with a CFTR mutation predicted to have residual function. A summary of mutations predicted to have residual function is in Section 10.8. This study is designed to evaluate (i) the efficacy and safety of TEZ/IVA and (ii) the efficacy and safety of IVA monotherapy in this patient population using an incomplete block design.

The treatment regimens are:

[figure not shown]
- TEZ/IVA combination treatment
  - Morning dose: 1 tablet fixed-dose combination of TEZ 100 mg/IVA 150 mg and 1 tablet IVA placebo
  - Evening dose: 1 tablet IVA 150 mg
- IVA monotherapy
  - Morning dose: 1 tablet placebo visually matched to the fixed-dose combination tablet and 1 tablet IVA 150 mg
  - Evening dose: 1 tablet IVA 150 mg
- Placebo
  - Morning dose: 1 tablet placebo visually matched to the fixed-dose combination tablet and 1 tablet placebo visually matched to IVA 150 mg
  - Evening dose: 1 tablet placebo visually matched to IVA 150 mg

This study includes a Screening Period (approximately 28 days), Treatment Period 1 (8 weeks), Washout Period (8 weeks), Treatment Period 2 (8 weeks), and Safety Follow-up Visit (approximately 28 days). Approximately 204 subjects (34 per sequence) will be enrolled and stratified by age at the Screening Visit (<18 versus  $\geq$ 18 years of age), FEV1 severity (determined during the Screening Visit; <70% versus  $\geq$ 70% predicted), and type of residual function mutation on the second CFTR allele (Class V non-canonical splice mutation versus Classes II to IV residual function mutation; see Section 10.8), and then randomized (1:1:1:1:1:1) to 1 of the 6 treatment sequences, as shown in Figure 6-1. A minimum of 25% of enrolled subjects will carry a Class II to IV mutation on the second CFTR allele. Stratification of enrollment will be managed through the interactive web response system (IWRS). Enrollment into the non-canonical splice strata will be limited to no more than 75% of total enrollment.

- Sequence 1: TEZ/IVA in Treatment Period 1 → washout → IVA monotherapy in Treatment Period 2
- Sequence 2: IVA monotherapy in Treatment Period 1 → washout → TEZ/IVA in Treatment Period 2

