#### **8.4.1.8 Summaries of Respiratory Events, Respiratory Symptoms and Elevated Transaminase by Treatment Interval**

Respiratory events, Respiratory symptoms and elevated transaminase will also be summarized by the following treatment interval:

- 0-1 Weeks: [Day1, Day7]
- >1 -2 Weeks: [Day8, Day14]
- >0 -8 Weeks: [Day1, Day56]
- >8 Weeks: [Day57, end of TE period])

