### **If only Day of AE start date is missing:**

If the AE start year and month are the same as that for the first dose date, then:

- If the full (or partial) AE end date is NOT before the first dose date or AE end date is missing, then impute the AE start day as the day of first dose date; otherwise, impute the AE start day as 1.
- Otherwise, impute the AE start day as 1.

Compare the imputed AE start date with TE period to determine whether the AE is pretreatment AE, TEAE or post-treatment AE.

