### **If Year of AE start date is missing:**

If the year of AE start is missing or AE start date is completely missing then query site with no imputation. Also compare the full (or partial) AE end date to the first dose date. If the AE end date is before the first dose date then the AE should be considered as a pretreatment AE. Otherwise, the AE will be considered as TEAE.

The imputation rule will be applied with respect to treatment start date for both periods and preference will be given to treatment in period 1 in case the AE is assigned to treatments in both periods. Missing or partially missing AE end date will not be imputed.

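### SAP 8.4.1 assigns a partially dated AE to the Period 1 treatment even when its recorded month lies in Period 2; SAP 10.7 does not, and the SAP does not say which governs

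*SAP*

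**What the plan says.** SAP 8.4.1 contains three statements that bear on this point.

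- Attribution: if an AE starts or worsens during a Treatment Period, "this AE will be attributed to the treatment the subject was receiving during the Treatment Period".
- Default for missing or partial start dates, unless there is clear evidence of pre-dose onset or worsening: "the start date will be imputed to the first dosing date and the AE assigned to the treatment in Treatment Period 1". Protocol 12.3.4.1 has the same sentence.
- Cross-reference: "As an intermediate step for programming purposes, imputation rules for missing or partially missing AE start/end dates are defined in Section 10.7".

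SAP 10.7 works differently. If only the day is missing, the day becomes the first-dose day when the recorded month is the first-dose month and the AE did not end before that dose; "otherwise, impute the AE start day as 1". The next instruction is: "Compare the imputed AE start date with TE period to determine whether the AE is pretreatment AE, TEAE or post-treatment AE". For the crossover, "The imputation rule will be applied with respect to treatment start date for both periods and preference will be given to treatment in period 1", the preference applying only where the AE is assigned to both periods. If the year is missing, no date is imputed; the AE is treatment-emergent unless it ended before the first dose.

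**The concern.** A start month recorded in Period 2 is a partial date and is no evidence of pre-dose onset, so the 8.4.1 default applies to it. The AE is then dated to study Day 1 and given to the Period 1 treatment. That contradicts the attribution rule in 8.4.1 itself and the result of 10.7.

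The design makes this matter. Subjects are "then randomized (1:1:1:1:1:1) to 1 of the 6 treatment sequences", and no sequence repeats a treatment, so a wrong period always means a wrong treatment column. If 8.4.1 is programmed literally, Period 2 events with partial dates move

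- from an active treatment to placebo in sequences 4 and 6,
- from placebo to an active treatment in sequences 3 and 5,
- between the two active treatments in sequences 1 and 2.

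Safety of each active regimen is a secondary objective, and the TEAE tables are by treatment. The interval tables in SAP 8.4.1.8 (respiratory events, respiratory symptoms, elevated transaminase) are affected as well, because every partial date would fall on Day 1.

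**Working it through.** The plan states no figure on this point, so I applied the two rules as written.

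**One case.** First dose 10 Jan 2016, nominal schedule, AE start recorded as June 2016.

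- TE Period 1 ends at the Week 12 visit (Day 85): 10 Jan + 84 days = 3 Apr.
- Period 2 first dose (Day 113): 10 Jan + 112 days = 1 May.
- TE Period 2 ends 28 days after the last dose (Day 168 + 28 = Day 196): 10 Jan + 195 days = 23 Jul.
- SAP 8.4.1: 10 Jan, Period 1, Day 1.
- SAP 10.7: 1 Jun, which is study Day 144, so Period 2 Day 144 − 112 = 32.

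In sequence 4 this is placebo against TEZ/IVA; in sequence 3 it is TEZ/IVA against placebo.

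**All cases with month and year known and onset in Period 2.** Inputs: TE Period 1 = Days 1 to 85 and TE Period 2 = Days 113 to 196 (Protocol Table 3-2, SAP 8.1). Assumptions: onset day equally likely within the TE period, first-dose dates spread evenly over a four-year calendar cycle (1,461 dates), and AE end date missing or not before the first dose. That gives 1,461 × 84 = 122,724 cases. Section 10.7 was run once against each period start.

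| Result | Cases | Share |
|---|---|---|
| 8.4.1 gives Period 2 | 0 | 0% |
| 10.7 gives Period 2 on both runs | 101,204 | 82.5% |
| 10.7 gives post-treatment on one run, Period 2 TEAE on the other | 21,303 | 17.4% |
| 10.7 gives Period 1 (month begins inside TE Period 1; tie-break applies) | 217 | 0.2% |

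Shares are rounded. With the Week 12 visit 5 days late, the Period 1 share rises to 1.2%. With that visit 5 days early, or the washout 7 days longer, it is 0%.

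The 17.4% arises when the recorded month contains both gap days and the Period 2 first dose. Example: first dose 4 Jan 2016, TE Period 1 to 28 Mar, Period 2 from 25 Apr, AE start April. The run against the Period 1 start gives 1 Apr, which lies in the gap (post-treatment). The run against the Period 2 start gives 25 Apr (Period 2 TEAE). The tie-break covers only an AE assigned to treatments in both periods, so it does not decide this case.

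**Interval tables.** I counted days from the first dose of the period, which 8.4.1.8 does not spell out, and took a Period 1 TEAE to override a pre-treatment result on the other run. Under 8.4.1 all partial dates fall in the first-week row. Under 10.7, of month-known Period 1 onsets, 31,747 of 1,461 × 85 = 124,185 do, or 25.6% (24.1% to 27.2% over the Week 12 window). So for about 74% of these onsets the interval row can differ although the treatment agrees.

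**Where the rules agree on treatment.** Fully missing dates, and year-only dates in the first-dose year, go to Period 1 under both rules when the AE did not end before the first dose. Year-only dates conflict only when that calendar year begins after TE Period 1 has ended.

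**The case against.** The strongest defence is that 8.4.1 only summarizes and 10.7 is the working rule. The sentence after the default sends the programmer to 10.7, which is detailed and covers both periods. SAP 8.2.4 uses the same phrase about an intermediate step to introduce the coded rule for medication dates. This reading is plausible and may be the intent. But no sentence gives precedence, and on this reading the summary misstates the rule it summarizes. The clause that the SAP prevails over the protocol does not help, because the conflict lies within the SAP.

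The second defence is materiality, and most of it stands. AEs are asked about at each visit, the onset date is a required field, and missing data are queried. The safety analysis is descriptive, with no testing. All percentages above are shares of partial dates, not of all AEs.

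A reader might infer that 10.7 on its own already places practically all of these AEs (82.5% + 17.4%) in Period 2, so that a bare reference to it would be enough. The documents do not support that: the 17.4% needs a precedence that 10.7 does not state. A bare reference would also drop the exception for clear evidence of pre-dose onset or worsening, since 10.7 looks only at the AE end date.

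**Conclusion.** The conflict is real. For a start month recorded in Period 2, the 8.4.1 default never gives Period 2. Section 10.7 gives it in 82.5% of cases without further assumption, and in up to 99.8% if a Period 2 TEAE overrides a post-treatment result. These shares rest on the nominal schedule, evenly spread first-dose dates and uniform onset; the direction of the conflict does not depend on them.

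A reader might infer a bias in favour of the active treatments. The documents do not support that: with equal allocation to six sequences, the misclassification runs in both directions and mixes the columns. Nor do they support a claim that the TEAE tables would change visibly, because the number of partial dates is not given and is probably small. No hypothesis test is affected. The text should be corrected because, followed literally, a stated rule puts AEs under the wrong treatment, and the correction is cheap.

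**What to change.** In SAP 8.4.1, keep the clause on clear evidence of onset or worsening before the first dose. Replace the rest of the sentence with: *Otherwise, missing or partial AE start dates are imputed, and the AE is assigned to a period, according to Section 10.7, which governs; the Period 1 default applies only when the available date parts do not identify a period.* Delete the opening words of the next sentence that call 10.7 an intermediate programming step.

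In SAP 10.7, add two statements:

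- When the recorded month contains both gap days and the Period 2 first dose, and the two runs give post-treatment and Period 2 TEAE, the AE is assigned to Period 2. This is the conservative choice for a TEAE table. Its downside is that some gap onsets, which 8.4.1 defines as post-treatment, are counted as Period 2 TEAEs: on the nominal schedule, 46% of month-known gap onsets. The other 54% already go to Period 1 under 10.7.
- How AEs with a fully missing start date enter the 8.4.1.8 intervals, since 10.7 classifies them but imputes no date.

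The cost is a few sentences of SAP text and little programming beyond the 10.7 rules already specified. Protocol 12.3.4.1 need not be amended, because the SAP Introduction says that the SAP prevails where methods differ. The change should be made before database lock and unblinding, so that attribution is not chosen with results in view.

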#### 8.4.1.1 Overview of Treatment Emergent AEs

An overview of all TEAEs will be summarized in the following categories:

- Any TEAEs
- TEAEs by relationship
- Related TEAEs
- TEAEs by severity
- Grade 3/4 TEAEs
- Serious TEAEs
- Related Serious TEAEs
- TEAEs leading to treatment discontinuation (this will include TEAEs leading to discontinuation of either TEZ/IVA tablet or the IVA tablet)
- TEAEs leading to treatment interruption (this will include TEAEs leading to interruption of either TEZ/IVA tablet or the IVA tablet)
- TEAEs leading to death

#### **8.4.1.2 TEAEs and TE SAEs by System Organ Class and Preferred Term**

The number and percentage of subjects with TEAEs will be summarized by treatment group, MedDRA system organ class (SOC) and preferred term (PT), where multiple occurrences of the same AE for the same subject will be counted only once. The summary table will be presented in descending order of frequencies in the TEZ/IVA treatment group. TE SAEs will be summarized similarly.

#### **8.4.1.3 TEAEs and TE SAEs by PT**

The number and percentage of subjects with TEAEs will be summarized by treatment group and PT, where multiple occurrences of the same AE for the same subject will be counted only once. TE SAEs will be summarized similarly.

#### **8.4.1.4 Related TEAEs and TE SAEs by SOC, PT**

The number and percentage of subjects with related TEAEs will be summarized by treatment group, SOC, and PT, where multiple occurrences of the same AE for the same subject will be counted only once. The summary table will be presented in descending order of frequencies in the TEZ/IVA treatment group. TEAEs in the following relationship to study drug regimen categories will be considered as related: Related, Possibly Related and Missing. TE SAEs will be summarized similarly.

#### **8.4.1.5 Grade 3/4 TEAEs by SOC, PT**

The number and percentage of subjects with Grade 3/4 TEAEs will be summarized by treatment group, SOC, and PT, where multiple occurrences of the same AE for the same subject will be counted only once. The summary table will be presented in descending order

of frequencies in the TEZ/IVA treatment group. Grade 3/4 TEAEs include severe and life-threatening adverse events.

